Using this approach, it is expected to address the informatics challenge of determining how to design information technology that improves engagement and clinical outcomes for patients who require continuous monitoring and who engage an informal caregiver in self-management outside clinical settings. Our work extends the design of remote-monitoring systems from stationary, home-based systems to wearable devices that patients can engage with throughout an active day in the community. Our research team—which consists in a biomedical systems engineer, a human factors engineer specialized in consumer health informatics, a pediatric endocrinologist, and a pediatrician specialized in clinical research — works in alliance with the Center for Diabetes Technology at the University of Virginia. Study team members have developed this ambulatory platform that will be used as the foundation for this study.

Rationale: The hypothesis of this study is that individuals randomized to the CGM/Fitbit with no weekly feedback (Control Group) will improve management modestly initially (as a result of either of new access to CGM or the Hawthorne effect of being studied), but their measures of engagement (patient self-management behavior (i.e. personal insulin parameters) and diabetes-related dyad communication) will return to baseline levels by the 12-week evaluation. By contrast, it is hypothesize that individuals randomized to CloudConnect (Experimental Group) will have a greater increase in engagement and dyad communication by 8 weeks that is sustained by 12 weeks (3 months).

It is further hypothesize that adolescents randomized to CloudConnect will have a lowering of HbA1c that is related to the increase in dyad disease-specific engagement. Moreover, our hypotheses are that this unique self-management approach in T1D will increase engagement of adolescents and their informal caregiver through increased communication and self-management behavior, and that this increase in engagement will lead to improved medical outcomes.

These hypotheses are based on data from preliminary studies collected by the study group and the literature. This preliminary data support that parents of adolescents with T1D are eager to follow their child's blood

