glucose tracing via remote monitoring — suggesting potential for an increase in involvement with such access and increase in disease-related communication. It is well described that an increase in parental involvement in diabetes control is associated with better medical outcomes such as lower HbA1c. Similarly, when adolescents exhibit increased degrees of participation in their care (such as a subset of adolescents who regularly used their CGM in a large-scale trial), this is associated with a lowering of HbA1c.

We will test these hypotheses using a randomized trial of CGM/Fitbit with no weekly feedback vs. CGM/Fitbit to CloudConnect. In addition to being compared against each other, both approaches will be compared to degree of engagement and efficacy of diabetes control experienced prior to the intervention, this information will be obtained at baseline. This randomized trial of CloudConnect in a chronic disease setting has been designed to assess changes in personal and dyad engagement and the relationship between this engagement and an important disease outcome.

Study Design: Biomedical

1. Will controls be used?

Yes

► IF YES, explain the kind of controls to be used.

The Control Group adolescent subjects will have the same inclusion/exclusion criteria and same characteristics as the Experimental Group adolescent subjects. The Control Group participants will use the study CGM, but subjects may elect not to set alarms or use the CGM Apps. This group will also use a study activity tracker (i.e Fitbit). Control subjects will use their personal insulin parameters throughout the trial. Control Group participants will use study insulin pen at mealtime with their home insulin. Control Group subjects will download their study equipment and provide it to the study team each week. The Control Group will **not** receive a weekly CloudConnect Report from the study team. Follow up visit in-clinic and phone calls, text messages and or/email will be the same as the Experimental Group.

2. What is the study design?

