Study Objectives & Endpoint Definitions:

As mentioned previously, this project seeks to assess how CloudConnect affects participant engagement, dyad engagement, and clinical outcomes in adolescent T1D.

We will assess how adolescents and their parent(s)/guardian(s) respond to this new approach using the Family Communication Inventory (FCI). This diabetes-specific approach was designed by the investigators to assess parent-child communication regarding tasks (discussion of insulin dosing for a given meal, BG trends, need for dose changes). As an outcome measure, scores for parents and adolescents are summed, with higher scores representing higher degree of engagement and T1D-specific communication.

Power/Precision of the study to address major study endpoints:

In using the FCI, we determined based on preliminary data from 220 adolescent/parent participants eligible for the study, with mean (90.3) and standard deviation (12.5) that we are powered to detect a difference of 8.5% in this outcome in the treatment group with 80% power and an alpha of 0.05. This study will require 40 adolescent participants with 40 parent(s)/guardian(s) to complete per arm. Assuming a non-adherence/drop-out rate of 20-30% for Intention-to-Treat (ITT) analysis, 55 participants is yielded per arm.

3. Provide a justification for the sample size used in this protocol.

The study team will attempt to enroll an equal number subjects based on gender, CSII, and MDI use. The study is powered to detect a difference of 8.5% in this outcome in the treatment group with 80% power and an alpha of 0.05. This study will require 40 adolescent participants with 40 parent(s)/guardian(s) to complete per arm. Assuming a non-adherence/drop-out rate of 20-30% for Intention-to-Treat (ITT) analysis, 55 participants is yielded per arm.

4. What is your plan for primary variable analysis?

Because this is a randomized study, our primary outcome (score on the Family Communication Inventory) will be by t-test comparing those randomized to CloudConnect to usual care+CGM. Comparison of secondary outcomes between treatment groups will also be t-tests. Secondary analyses of both the primary and secondary outcomes will utilize multivariable ANOVA, particularly in the event that key variables differ between groups. For example, if average steps per day [as a measure of exercise] is higher in one group vs.

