 - On a scale of 1-7, with 1 being not at all useful and 7 being very useful, how useful were the weekly reports in helping you communicate with your parents/child about managing your/your child's diabetes? Can you tell me why you gave the score you did? What could have made the weekly reports more useful to you?
 - Is there anything else you would like to tell us about your experience with the weekly reports?

The weekly contact by phone, email or text for both the Control and Experimental Groups will be to:

- Check for AE or SAE
- Remind to download all the data (i.e. CGM, insulin pump/insulin pen, Fitbit data)
- Ask standardized questions, which will include the following:
 - For the child participant:
 - During the past week, did you talk with your parents about your diabetes management?
Yes or No
 - If you answered "yes," how good or bad was the tone of that conversation?
(Likert scale: Very good good Neutral bad Very bad)
 - During the past week, did you change your insulin parameters?
(Yes=1, No=2)
 - For the adult participant:
 - During the past week, did you talk with your child about his/her diabetes management?
Yes or No
 - If you answered "yes," how good or bad was the tone of that conversation?
(Likert scale: Very good good Neutral bad Very bad)
 - During the past week, did your child change his/her insulin parameters?
(Yes=1, No=2)

(Yes=1, No=2)

Visit 1: Adolescent subjects will be screened as indicated in the inclusion/exclusion criteria, and the consent form will be signed electronically after all the question related to the study are answered. The consenting process may occur over the phone/video or in-person. Demographic information and medical history information will then be obtained. A physical exam can either be performed at Visit 1 or documentation of a physical exam at a physician/provider visit within one year will suffice. Hemoglobin A1c will be collected with point-of-care equipment or at a local laboratory. This can be omitted if it is not possible to go to a laboratory or come to the clinic because of governmental restrictions such as Stay-at-Home orders. A urine pregnancy test will be required for adolescent girls who are able to become pregnant. Test must be negative to participate in the study.

If the adolescent subject meets eligibility, visit 1 and 2 may be combined. A repeat Hemoglobin A1c will be collected if visit 1 and 2 are greater than 28 days.

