Visit 4 – End of Study (about Week 12): Subjects will be asked to return to the Clinical Research Unit (CRU) to return study equipment (i.e. Bluetooth pen, CGM, Fitbit), if possible. A post-study HbA1c test will be obtained with a point-of-care equipment or local laboratory (same method as screening collection). This can be omitted if it is not possible to go to a laboratory or come to the clinic because of governmental restrictions such as Stay-at-Home orders. Questionnaires will be completed electronically at the end of this visit. Questionnaires may be completed at home prior to this visit or at the CRU.

2. If this protocol involves study treatment, explain how a subject will be transitioned from study treatment when they have completed their participation in the study.

The study intervention is to evaluate the communication between the adolescent study subjects and their parents. The treatment for T1D is subcutaneous insulin either by using insulin pumps or insulin pens. This

treatment will remain the same at the completion of this study. Subjects will return to using their personal diabetes equipment and follow their own insulin parameters.

Subject Compliance with Study Procedures

- 1. Explain how the study team will monitor the subject for compliance with the study procedures.** A mid-study visit during Week 8 is planned to assess compliance. In addition, there will be at least 1 phone call or text message per week to remind subjects to download and transmit the required data, if needed.

It will be at the discretion of the investigator to determine if the patient is not compliant, i.e. three or more weeks with no data received, and the subject will be withdrawn for the study and replaced.

- 2. Describe criteria for when a subject is considered to be non-compliant with study procedures.**

The subject will be dismissed for the study if the subject misses 3 or more weeks of data downloads.

Bibliography

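### HbA1c is hypothesised to fall from baseline, but its analysis is an unadjusted between-arm t-test on an undefined quantity; ANCOVA on the baseline value already scheduled would be more precise at almost no cost

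*Combined protocol and SAP*

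**What the plan says.** **Hypothesis.** The Rationale under Objectives/Hypothesis predicts that "adolescents randomized to CloudConnect will have a lowering of HbA1c that is related to the increase in dyad disease-specific engagement", and more generally that "this increase in engagement will lead to improved medical outcomes". It goes on to say that "both approaches will be compared to degree of engagement and efficacy of diabetes control experienced prior to the intervention", with the prior information obtained at baseline. No method for that comparison is given.

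**Analysis.** Under Statistical Considerations, item 4 says "Comparison of secondary outcomes between treatment groups will also be t-tests". Item 5 puts HbA1c first in the list of secondary variables. It gives no time point, does not say whether the final level or the change is meant, and names no baseline term. Item 4 adds: "Secondary analyses of both the primary and secondary outcomes will utilize multivariable ANOVA, particularly in the event that key variables differ between groups". The examples given there are steps per day and the proportion of participants on multiple daily injections.

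**Data.** At Visit 1, "Hemoglobin A1c will be collected with point-of-care equipment or at a local laboratory", with a repeat if Visits 1 and 2 are more than 28 days apart. For Visit 4, at about week 12, the text reads: "A post-study HbA1c test will be obtained with a point-of-care equipment or local laboratory (same method as screening collection". At both visits an exception applies: "This can be omitted if it is not possible to go to a laboratory or come to the clinic because of governmental restrictions".

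**The concern.** HbA1c is the only clinical measure that the Rationale names with a direction. Both the hypothesis and the promised comparison refer back to the value before the study, but the analysis plan does not use that value.

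Two things follow. First, the endpoint is open. In an open-label trial, an analyst could choose between final level and change after seeing the data. Second, whichever is chosen, an unadjusted t-test gives up precision that a measurement already being taken would supply. It also leaves the estimate exposed to a chance difference in starting HbA1c. Randomisation is stratified by age group and insulin therapy only, so the design does not balance HbA1c directly.

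At stake is a real difference in HbA1c that is missed, or an estimate shifted by chance imbalance, on the outcome meant to show clinical benefit.

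**Working it through.** **1. The plan's own figure.** The only sample-size statement concerns the Family Communication Inventory (FCI): mean 90.3, SD 12.5, a difference of 8.5%, 80% power, alpha 0.05, 40 completers per arm. Sidedness is not stated; two-sided is assumed here.
- Difference: 0.085 × 90.3 = 7.68 points.
- n per arm = 2 × (1.960 + 0.842)² × 12.5² / 7.68² ≈ 41.6, so 42 (43 by the exact t-test).
- Power at 40 per arm: 78.4% by the normal approximation, 77.4% exact.

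This reproduces the stated 40 to within a few participants. It says nothing about HbA1c, for which no power is claimed.

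**2. Residual SD for HbA1c.** Let S be the HbA1c SD, taken as equal at both times, and r the correlation between baseline and final value. The documents give neither, so results are in units of S over a range of r.
- t-test on final level: S
- t-test on change: S × √(2(1 − r))
- ANCOVA on baseline: S × √(1 − r²)

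ANCOVA is below the level test for any non-zero r. It is below the change test for any r under 1, because the ratio of the two SDs is √((1 + r)/2).

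**3. Detectable difference and power.** With 40 per arm, two-sided 0.05 and 80% power, the noncentral t gives 0.634 residual SDs. For example, at r = 0.7 ANCOVA detects 0.634 × √(1 − 0.49) = 0.634 × 0.714 = 0.453 S. The degrees of freedom that ANCOVA uses are ignored.

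| r (assumed) | Detectable: level | Detectable: change | Detectable: ANCOVA | Power at 0.5 S: level | Power at 0.5 S: change | Power at 0.5 S: ANCOVA |
|---|---|---|---|---|---|---|
| 0.3 | 0.634 | 0.751 | 0.605 | 60% | 46% | 64% |
| 0.5 | 0.634 | 0.634 | 0.549 | 60% | 60% | 72% |
| 0.6 | 0.634 | 0.567 | 0.507 | 60% | 70% | 79% |
| 0.7 | 0.634 | 0.491 | 0.453 | 60% | 81% | 87% |
| 0.8 | 0.634 | 0.401 | 0.381 | 60% | 94% | 96% |

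Against the level test, ANCOVA lowers the detectable difference by about 5% at r = 0.3, 13% at 0.5, 29% at 0.7 and 40% at 0.8. A change score improves on the level only when r exceeds 0.5. If S were 1.0 HbA1c percentage point (an assumption), the detectable differences read directly as points.

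**4. Chance imbalance.** The difference between arms in mean baseline HbA1c has standard error S × √(2/40) = 0.22 S. A gap of up to 1.96 × 0.224 = 0.44 S is therefore within the usual 95% range. A gap g shifts the level comparison by r × g and the change comparison by −(1 − r) × g. For g = 0.3 S the shifts are +0.15 S and −0.15 S at r = 0.5, and +0.09 S and −0.21 S at r = 0.3. ANCOVA removes this expected shift.

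**The case against.** The strongest reply is that the plan does not go wrong so much as stay silent. Four stronger readings are tempting, and the documents do not support them.

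- **That the plan analyses HbA1c as a raw final level.** It never says so. A t-test on change fits items 4 and 5 equally well. The defect is an undefined endpoint.
- **That the t-test is biased, or tests a different between-arm effect.** Under randomisation, t-tests on level and on change target the same between-arm difference, and alpha already allows for chance imbalance. The loss is in precision and in protection from the imbalance that actually occurs.
- **That imbalance would distort the level but not the fall.** Step 4 shows that it enters the change with the opposite sign.
- **That the final value mostly reflects where each adolescent started.** The share of variance explained is r²: 9%, 25%, 36%, 49% and 64% at the five correlations. It exceeds half only at 0.8. The 7–11% entry range could also lower r.

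The reply can also point to the secondary multivariable ANOVA, which covers secondary outcomes and could take baseline HbA1c as a covariate. That is a partial answer. The analysis is secondary, it is intended mainly for cases where key variables are found to differ, and it never names the baseline value of the outcome.

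It is also fair to say that HbA1c is secondary and unpowered, that the gain at r = 0.3 is small (64% against 60%), and that the Rationale predicts better medical outcomes in general. These points limit the weight of the concern. They do not supply the missing definition or a reason to leave baseline out.

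**Conclusion.** The point holds as a low-cost improvement together with a gap in definition. The hypothesis and the promised baseline comparison have no counterpart in the analysis section, which names an unadjusted t-test on an undefined HbA1c quantity while both measurements are scheduled.

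For a 0.5 SD difference, ANCOVA raises power from 60% for a level t-test to between 64% and 96% as r runs from 0.3 to 0.8. The size of the gain depends on assumptions: two-sided alpha 0.05, equal SDs at both times, the assumed r, and a final HbA1c for all 40 per arm. The last may fail, because Visit 4 allows the test to be omitted. The direction of the gain does not depend on the particular r chosen within that range.

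The FCI sample size is unaffected. The adjusted between-arm difference does not itself test the link between HbA1c and engagement, or a fall within one arm.

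**What to change.** In Statistical Considerations, items 4 and 5:

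1. Define the outcome as end-of-study HbA1c, at about week 12.
2. Compare arms by ANCOVA with the pre-randomisation HbA1c as covariate, using the repeat value where the gap between Visits 1 and 2 requires one. Report the adjusted difference with its confidence interval.
3. Keep participants whose baseline HbA1c was omitted under the governmental-restriction exception in the model, with a missing-baseline indicator.
4. State how a final HbA1c omitted under the same exception at Visit 4 will be handled.

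If the link between HbA1c and engagement is to stay among the hypotheses, it needs its own stated analysis, since this model does not test it.

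The cost is a wording change and one or two degrees of freedom: one for baseline and one for the indicator. No new measurement, visit or participant is needed.

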This is a randomized control, open-label, single-site clinical trial. We will target completion by eighty adolescents (age 12-17 years) with Type 1 diabetes and their parent/guardian (age 18+) to participate in a 3 month outpatient study. Participants will be randomized to either a Control Group or Experimental Group. Both groups will use the study continuous glucose monitor, study activity tracker, and a study insulin pen if an multiple daily injection (MDI) user. Subjects who use an insulin pump to treat their type 1 diabetes will use their personal insulin pump. All subjects will be asked to download this equipment and provide it to the study team each week. The study team will communicate weekly with each group. Questionnaires will also be completed at the beginning and at the end of the study. The Experimental Group will receive the CloudConnect Reports. The Control Group will not receive this feedback.

3. Does the study involve a placebo?

No

Human Participants

Ages: 12-17 years old and at least one of parent(s)/guardian(s) (age 18+)/guardian (adolescent/parent dyad is required for participation in this trial)

Sex: Male and Female

Race: All

1. Provide target # of subjects (at all sites) needed to complete protocol.

For the Pilot Study, up to 6 adolescents and 6 parent(s)/guardian(s) may complete the study. These pilot subjects may also participate in the Main Study.

For the Main Study, 160 subjects (80 dyads – consisting of 80 adolescents and 80 adults) need to complete the study.

2. Describe expected rate of screen failure/ dropouts/withdrawals from all sites.

We expect that because the length of the study it could be 20-30% dropouts/withdrawals from the study.

3. How many subjects will be enrolled at all sites?

This is a single site clinical trial to be completed at UVa.

4. How many subjects will sign a consent form under this UVa protocol?

Up to 210 subjects (105 dyads – consisting of 105 adolescents and 105 parent(s)/guardian(s)) will sign consent for the Main Study and up to 16 subjects (8 parent/child dyads) will sign a consent for the Pilot Study. i.e. total = 226 (210+16)

Inclusion/Exclusion Criteria

1. List the criteria for inclusion for Pilot and Main Study Adolescent Subjects

- Willingness to provide informed consent
- Adolescents ages ≥ 12 and ≤ 17 years old with a parent/guardian (18+ yo) who is willing to participate with the child

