another, this will be used as a variable in the comparison of mean glucose by CGM to evaluate whether there remained a difference in mean glucose once total daily steps was taken into account. Similarly, if there is an imbalance of key participant characteristics among participants who complete the study in one treatment group (such as higher proportion of multiple-daily-injection participants in the CloudConnect group), this will be considered as a variable in the multivariable ANOVA comparing mean glucose by CGM, as a secondary analysis.

5. What is your plan for secondary variable analysis?

- HbA1c
- Mean glucose by CGM
- Percent time in range 70-180 mg/dL
- Percent time in range 70-150 mg/dL
- Percent time <70 mg/dL
- Percent time >180 mg/dL
- Number of low BG
- Average daily insulin dose
- Average grams of carbohydrate entered
- Steps/day by Fitbit
- Questionnaires: Family Conflict Scale, Division of Diabetes Responsibilities, Child Self Management and My-Q scores.
- Response to weekly standardized questions:
 - i. *During the past week, did you talk with your parents about your diabetes management?*
(Yes=1, No=2)
 - ii. If you answered “yes,” how good or bad was the tone of that conversation?
(Likert scale: Very good = 1; good =2; Neutral = 3 bad =4; Very bad =5)
 - iii. During the past week, did you change your insulin parameters?
(Yes=1, No=2)

6. Have you been working with a statistician in designing this protocol?

No

7. Will data from multiple sites be combined during analysis?

No

Study Procedures-Biomedical Research

1. What will be done in this protocol?

PILOT STUDY:

Up to six adolescent subjects and six parent(s)/guardian(s) will be enrolled in a Pilot Study to assess the components used by the Experimental Group of the Main Study. This trial will evaluate if: (i) subjects can be trained to use study CGM + study Fitbit + personal pump (if pump user) or study insulin pen for mealtime

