bolus treatments (if MDI) + CloudConnect component which consist of a weekly report based on analysis of the data gathered for each participant; (ii) subjects are able to upload all the data that the team needs to generate the CloudConnect report; (iii) the study team receives the necessary data in a convenient and timely fashion in order to produce the report. Participation in the Pilot Study may be up to three weeks. Both continuous subcutaneous insulin infusion (CSII) and Multiple Daily Injection (MDI) subjects are eligible to participate in this study. Pilot Study participants may participate in the Main Study.

Parent/Guardian Role:

The study team will ask one parent to serve as the 'family spokesperson'. This parent will complete:

- the weekly questionnaires for consistency
- attend training sessions with subject
- download data to study team each week
- participate in the weekly communication with their child (both parents will be encouraged to participated in the weekly communication)

This parent and the adolescent will also be available for contact by the study team (e.g. by phone/text/email) regarding study compliance issues such as uploading of data from CGM, insulin pump, insulin pen (if MDI subject), and activity monitor.

Participation in the study will be about 3 weeks.

Pilot Visits:

Visit 1: Screening Visit (up to 1 hour)

- Demographic information (date of birth, gender, race, and ethnicity)
- Medical and Diabetes History information
- A urine pregnancy test for adolescent girls who can become pregnant. The pregnancy test must be negative to participate.

If study eligible, subject will immediately proceed to Training Visit 2.

Visit 2: Device Training – (up to 1 ½ hours)

- Continuous Glucose Monitor Training – will be trained to use the Study CGM in its full capacity, including setting alarms
- Dexcom Apps Training (if interested in using) - App that will permit the parent(s)/guardian(s) to receive high or low glycemic value alarms
- Activity tracker (i.e. Fitbit) Training
- Study Insulin Pen Training if using Multiple Daily Injections to treat diabetes
- Download device instructions

Visit 3: Weekly Communication (3 weeks/21 days)

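### Pilot dyads who have already received CloudConnect reports may be randomised in the Main Study, including to Control; any carry-over there dilutes the primary comparison modestly and avoidably

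*Combined protocol and SAP*

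**What the plan says.** The permission appears twice, each time without a condition. Human Participants, item 1, sets the pilot size ("For the Pilot Study, up to 6 adolescents and 6 parent(s)/guardian(s) may complete the study") and adds "These pilot subjects may also participate in the Main Study". The Pilot Study text under Study Procedures repeats it: "Pilot Study participants may participate in the Main Study".

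The same Pilot Study text makes clear what these dyads receive. They are enrolled "to assess the components used by the Experimental Group of the Main Study", and the list of what is tested includes the "CloudConnect component which consist of a weekly report based on analysis of the data gathered for each participant". On duration: "Participation in the Pilot Study may be up to three weeks". The pilot training also covers CGM alarms and offers the apps. The Visit 3 text for the pilot mentions an Experimental Group, but no pilot randomisation or pilot control arm is described.

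In the Main Study, the report is what separates the arms. Study Design: Biomedical, item 2, says: "The Control Group will not receive this feedback". The Main Study procedures name the report, together with the alarms and apps, as the difference between groups.

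Nothing elsewhere deals with prior exposure:

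- The exclusion criteria bar active enrolment in another trial, not earlier receipt of CloudConnect.
- The inclusion criterion of one month on stable insulin parameters is not a washout from the reports.
- Statistical Considerations, item 1, stratifies by age and insulin therapy only.
- Items 2 to 5 of that section contain no rule that flags or sets aside pilot dyads.

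**The concern.** A pilot dyad randomised to Control has already had the thing that Control is defined by not having. If three weeks of reports change how a family talks about diabetes, and part of that change lasts to Week 12, the Control mean on the FCI rises and the estimated effect shrinks.

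There is a second, separate consequence. The closing paragraph of Objectives/Hypothesis says that both arms will also be compared with their own engagement before the intervention, as measured at baseline. For a pilot dyad in either arm, the Main Study baseline is not a pre-intervention measurement.

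At stake are a little power and a little attenuation in a trial with almost no margin at 40 completing dyads per arm.

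**Working it through.** **Inputs.** FCI mean 90.3, SD 12.5, difference 8.5%, 80% power, alpha 0.05 and 40 completing dyads per arm (Statistical Considerations, item 2). The primary test is a two-sample t-test (item 4). At most 6 pilot completers (Human Participants, item 1). The documents do not state sidedness; two-sided is assumed. Allocation is taken as 1:1.

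**The plan's own figure.** Difference Δ = 0.085 × 90.3 = 7.68 points; standardised, 7.68 / 12.5 = 0.614. The normal approximation needs 42 per arm and gives 78.4% power at 40. The t-test needs 43 per arm and gives 77.4% at 40. The stated 40 per arm for 80% is therefore roughly reproduced. The t-test value, 77.4%, is the reference below.

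**How many exposed dyads could reach Control.** Six of 80 is 7.5%. With a 40/40 split, strata ignored, 3 are expected in Control. If all six enter and complete, the chance that all six fall in Control is C(74,34) / C(80,40) = 1.3%. The chance that none does is the same by symmetry, so at least one is in Control with probability 98.7%.

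**Dilution.** Let k be the number of pilot dyads in Control and c the share of the CloudConnect effect that they still carry at Week 12. Then

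Δ_eff = Δ × (1 − c × k / 40).

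The SD is held at 12.5. The documents give no value for c, so a range is shown.

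| k in Control | c | Δ_eff (points) | Power, t-test, 40 per arm |
|---|---|---|---|
| any | 0% | 7.68 | 77.4% |
| 3 | 25% | 7.53 | 75.8% |
| 3 | 50% | 7.39 | 74.2% |
| 3 | 100% | 7.10 | 70.8% |
| 6 | 100% | 6.52 | 63.5% |

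Example, third row: 7.68 × (1 − 0.5 × 3/40) = 7.68 × 0.9625 = 7.39.

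**Does the raised baseline add bias between arms?** Let a pilot dyad's baseline be raised by b. In Control it ends at +w (with w = cΔ); in Experimental it ends at +Δ. The changes from baseline are w − b and Δ − b, and their difference is Δ − w. The term b cancels. What remains is the dilution already counted for the end-of-study score. Exposure precedes randomisation, so b is the same in both arms in expectation. Only the within-arm change is distorted, because it contains −b.

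**The case against.** The case for leaving this alone is reasonable, and several parts of it stand.

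- **Six is a ceiling.** Pilot dyads must consent again and meet the HbA1c entry range, which applies to the Main Study but not the pilot. They must then complete despite 20–30% expected dropout. Dropout alone leaves 6 × 0.7 to 6 × 0.8, or 4.2 to 4.8 completers, so about 2 in Control.
- **Full carry-over is extreme.** About three reports would have to produce the whole 12-week effect and hold it for 12 further weeks without reports. Nothing in the documents supports that. Their only statement on persistence, in the Rationale, expects Control's early gains (from new CGM access or from being studied) to be gone by Week 12.
- **The direction is conservative.** Dilution runs toward no effect, and randomisation stays intact.

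A reader might infer more than the documents support. One such inference is that a baseline raised by exposure biases any change-score or baseline-adjusted comparison of the arms. It does not, because the raised baseline is balanced in expectation and cancels. The planned primary analysis is in any case a t-test on the FCI score. Another is that the trial should expect power near 63.5%. That figure needs both full carry-over and a 1.3% allocation. A third is that the comparison is certainly contaminated. The permission is certain, but the harm depends on carry-over that the documents do not quantify.

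The objection does not remove the point. The rule admits exposed families to the unexposed arm without any safeguard, and nothing in the plan depends on admitting them.

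**Conclusion.** The point holds as a modest, avoidable weakness that should be corrected. With the expected 3 pilot dyads in Control, the detectable difference is between 92.5% (7.10 / 7.68) and 98% (7.53 / 7.68) of the planned one for carry-over from 100% down to 25%. Power falls by 6.6 points at 100%, 3.2 at 50% and 1.6 at 25%. With no carry-over there is no loss. HbA1c screening and dropout would make the numbers smaller.

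Separately, the within-arm comparison with baseline is not a pre-intervention comparison for any pilot dyad that enters.

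These sizes rest on assumptions: a two-sided test, 1:1 allocation, an unchanged SD, all six pilot completers entering and finishing, and the carry-over range. The conclusion that the rule can only weaken the primary comparison assumes that any carry-over acts in the direction the trial hypothesises.

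**What to change.** In Human Participants, item 1, and in the Pilot Study text under Study Procedures, replace the permission with: *Dyads who took part in the Pilot Study are not eligible for the Main Study.* Add the same line to the exclusion criteria. Fill the places with new dyads. A pilot dyad entering the Main Study would itself use one of the 105 consents, so one-for-one replacement leaves that ceiling unchanged, and 40 per arm keeps the planned 77.4% power.

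The cost is a one-sentence amendment and the loss of up to 8 dyads from the recruitment pool, since 8 may consent to the pilot even though at most 6 complete it.

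If some pilot dyads are already randomised, keep them in the primary analysis on the intention-to-treat basis that the plan names, and record pilot participation. Pre-specify a sensitivity analysis that excludes them. Pilot participation is fixed before randomisation, so this exclusion does not break the randomised comparison. The trial is open-label, so the rule must be set before outcomes are compared by arm. Dropping these dyads from the primary analysis without replacement is not the better route: six fewer dyads (37 per arm) gives 74.1% power, about the same as keeping them at 50% carry-over (74.2%). For the within-arm comparison with baseline, report results with and without them.
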